5.2.8. Portion size appropriateness

Participants will complete a computerised task in which they will be asked to select the portion size they consider appropriate to consume for the test foods (portion-manipulated main dishes: lunch and dinner). Food pictures start at 40 kcal and increase in 40 kcal increments up to 1000 kcal.

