6. STUDY PROCEDURE

To disguise the true purpose of the study, participants will be told that the study aims to investigate daily fluctuations in mood after accounting for lifestyle factors such as diet and sleep. To bolster the cover story, participants will complete mood ratings before and after eating each meal and computerised tasks assessing categorisation of positive versus neutral words at lunchtime during each study day. Participants will also complete a sleep quality questionnaire on each study day to distract from the focus on food intake. Data from mood and sleep measures will not be analysed.

Figure 1 presents the sequence of steps in the study that are described **Table 2**. Occasionally, exceptions to the general rule will be made in order to fit within a participant’s schedule.

[figure not shown]

Figure 1. Participants’ schedule

Table 2. Description of the study procedure

RECRUITMENT	
 ▪ Participants respond to recruitment materials via email/phone ▪ Information sheet sent over email with link to online pre-screening questionnaire (Qualtrics) ▪ Eligible participants are invited to a screening session in person to formally check that they meet the eligibility criteria
--------------------	--

SCREENING SESSION Informed consent	
 ○ Ensure participants have read information sheet and explain the study in more details ○ Measure height and weight ○ Confirm eligibility ○ Participants sign the consent form and keep a copy ○ Organise the study with the participants: 
 ○ Record contact information and preferred communication (text, call or email) ○ Organise individual schedule ○ Explain FitBit use and physical activity restriction ○ Discuss allowed food / drink ○ Participants complete the baseline questionnaire: 
 ○ Demographic questions ○ Portion size appropriateness ○ Stroop task

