FINAL SESSION	
 ▪ Participants return FitBit device and snack box ▪ Check if any additional foods/drinks consumed ▪ Battery of measures 
 ○ Barratt Impulsiveness Scale ○ Satiety responsiveness ○ Plate clearing tendencies ○ Perceived food insecurity ○ Resource availability in childhood ○ Food choice motives ○ Compensatory health beliefs ▪ Study experience questionnaire ▪ Debriefing: explain the purpose of the study, the cover story and provide opportunity to ask questions ▪ Financial compensation (£70)

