7.5. Secondary analyses

7.5.1. Mediation analyses

For each participant, we will compute the average daily energy intake in the larger portion condition minus average daily energy intake in the smaller portion size condition, referred below as the portion size effect (PSE).

We will first report and compare the individual measures of impulsivity, inhibition, portion size appropriateness, satiety responsiveness, plate clearing tendencies, perceived food insecurity, resource availability in childhood, food choice motives, and compensatory health beliefs for lower and higher SEP groups using means, standard deviations and T-tests. If we find individual differences for any of these measures between participants of lower and higher SEP, mediation analyses will be performed in order to examine the extent to which it mediates the effect of SEP on the PSE (**Figure 2**).

[figure not shown]

Figure 2. Mediation diagrams for the PSE. Indirect effect of SEP on the PSE through a mediator M = $c - c' = ab$.

The mediation will be tested by estimating the indirect effects of SEP on the PSE through all the potential mediators and testing their indirect effect using bias-corrected bootstrap. We will use the PROCESS macro (Model 4 – one mediator at a time and all together) in SPSS that provides asymmetric bias-corrected bootstrap confidence intervals for inference about the indirect effects using 5,000 bootstrap samples [38]. Mediation will be tested by determining whether or not the confidence intervals of the indirect effects estimates contain zero.

If we do not find evidence that the PSE is moderated by SEP or that our individual difference measures do not explain moderation by SEP, we will repeat the primary analysis replacing SEP with the individual measures, to examine whether any of the individual difference measures moderates the main effect of portion size on daily energy intake.

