9.3. APPENDIX C: SATIETY RESPONSIVENESS

		Strongly disagree 1	Disagree 2	Neither agree nor disagree 3	Agree 4	Strongly agree 5
1.	I often leave food on my plate at the end of a meal.					
2.	I often get full before my meal is finished.					
3.	I get full up easily.					
4.	I cannot eat a meal if I have had a snack just before.					

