9.4. APPENDIX D: PLATE CLEARING TENDENCIES

		Strongly disagree 1	Disagree 2	Neither agree nor disagree 3	Agree 4	Strongly agree 5
1.	I always tend to clear my plate when eating.					
2.	I normally finish eating when my plate is empty.					
3.	Before I start eating, I normally plan to finish the serving I am about to eat					
4.	I rarely leave food on my plate					
5.	It is normal for me to have very little food left or an empty plate at the end of a meal					

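### Seven of the nine candidate mediators are first measured after the portion size effect (PSE) is complete; for four of them the direction of any association is undetermined, so mediation or moderation should not be declared

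*Combined protocol and SAP*

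**What the plan says.** Section 7.5.1 names nine candidate mediators: "impulsivity, inhibition, portion size appropriateness, satiety responsiveness, plate clearing tendencies, perceived food insecurity, resource availability in childhood, food choice motives, and compensatory health beliefs". The PSE is each participant's daily intake in the larger-portion condition minus that in the smaller-portion condition. The SEP groups are first compared on each measure by t-test. Where they differ, "mediation analyses will be performed in order to examine the extent to which it mediates the effect of SEP on the PSE". The tool is PROCESS Model 4 with a bias-corrected bootstrap, and the rule is whether the interval for the indirect effect contains zero. If SEP does not moderate the PSE, or the measures do not explain that moderation, each measure replaces SEP in the primary analysis and is tested as a moderator.

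Timing is set in section 6, Table 2. At screening, the baseline questionnaire holds demographic questions, "Portion size appropriateness" and the Stroop task. The final session, after Study Days 1 and 2, holds the "Battery of measures". It starts with the "Barratt Impulsiveness Scale" and continues with satiety responsiveness, plate clearing, food insecurity, childhood resources, food choice motives and compensatory health beliefs. No earlier administration of these seven is described. The battery comes before the study experience questionnaire and the debriefing.

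Appendix C includes "I often leave food on my plate at the end of a meal". Appendix D includes "I always tend to clear my plate when eating".

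**The concern.** The model runs from SEP to the mediator to the PSE. For seven of nine mediators the schedule runs the other way: the PSE is complete before the mediator is recorded. Someone who has recently cleared, or failed to clear, the laboratory plates is then asked about clearing plates. If that experience colours the answer, the measure will correlate with the PSE even when the underlying trait has no effect on intake.

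Model 4 estimates the mediator-to-PSE path from that correlation, adjusted for SEP. The fallback interaction tests the same correlation without the adjustment. Both give the same answer whichever variable influenced the other. The sensitivity analyses in 7.4.2 cover aim guessing, outliers, alternative SEP measures, demographic differences, portion order and dishware. None addresses direction, and 7.5.1 carries no caveat. At stake is the secondary objective in section 2, which is to explain why the PSE varies with SEP.

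**Working it through.** **Plan's own figure.** Section 7.6 gives f = 0.175, within-subject correlation 0.7, two measurements, alpha 0.05 and N = 46. The noncentrality is f²·N·m/(1−ρ) = 0.030625 × 46 × 2 / 0.3 = 9.39, and power is 0.850. The stated 46 reproduces. The same f for the interaction implies a standardised SEP difference in the PSE of 2 × 0.175 × √(2/0.3) = 0.90. The 0.7 SD used below is an assumption somewhat under that.

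**Order of measurement.**

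- Before the PSE: portion size appropriateness, inhibition (2 of 9).
- After the PSE, with items close to laboratory eating: satiety responsiveness, plate clearing, food choice motives, compensatory health beliefs (4 of 9). The match is closest for plate clearing and satiety and loosest for food choice motives.
- After the PSE, with little plausible route for carry-over: childhood resources (before age 12), food insecurity (last 12 months), trait impulsivity (3 of 9).

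**False mediation.** There is no path from the measure M to the PSE.

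- PSE = 0.7·SEP + noise, with SEP coded 0/1, equal groups and N = 60.
- M = k·(standardised PSE) + √(1−k²)·noise + shift·SEP.
- A false positive is a bias-corrected bootstrap interval for the indirect effect that excludes zero. Section 7.5.1 does not state the interval level; 95% is assumed.
- The gate is the SEP t-test at p<0.01, the level that section 7 sets for secondary analyses.

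| k | no SEP shift on M | shift 0.5 SD | shift 0.5 SD, after gate |
|---|---|---|---|
| 0 | about 1% | about 5% | about 3% |
| 0.1 | about 2% | about 13% | about 7% |
| 0.2 | about 6% | about 32% | about 19% |
| 0.3 | about 9% | about 58% | about 34% |

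Simulation error moves individual cells by up to about three percentage points. Without a shift, at the plan's implied 0.90 SD, the ungated figures are about 6% at k = 0.2 and 15% at k = 0.3.

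**False moderation.** With two conditions, the interaction of portion size with a continuous M is the test of the correlation between M and the PSE. For an M otherwise unrelated to the PSE, the Fisher approximation gives power ≈ Φ(atanh(k)·√(N−3) − 2.576) at p<0.01. With N = 60, √57 = 7.55:

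- k = 0.1: Φ(0.757 − 2.576), about 3%
- k = 0.2: Φ(1.531 − 2.576), about 15%
- k = 0.3: Φ(2.337 − 2.576), about 41%

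Simulation gives 3–4%, 16–18% and 40–44%, against 1% at k = 0. With N = 46, √43 = 6.56, and the same formula gives about 3%, 11% and 29%.

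**The case against.** The strongest reply is that carry-over may be slight. The PSE is a difference in whole-day intake, including breakfast, snacks, dessert and reported extras. Second helpings are available, and the two days are one to six weeks apart. Participants never see their own difference score, and a participant can clear both plates and compensate later. The items ask about habits, not about the study days. This stands as a reason to doubt the larger values of k. At k = 0.1, false mediation after the gate is about 7% against 3% with no carry-over.

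The second reply is that late placement protects a disguised experiment. Asking beforehand about plate clearing, or about balancing a small meal with a larger one, could prime compensation or reveal the aim, and that would touch the primary outcome. The documents do not give this reason. Screening already asks participants to "select the portion size they consider appropriate to consume for the test foods". Even so, one such task does not make four more scales harmless, and excluding aim guessers does not remove reactivity in those who do not guess. The trade-off is real.

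Stronger readings that a reader might infer are not supported:

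- **All seven late measures are compromised.** The content and recall periods of childhood resources, food insecurity and impulsivity make this implausible.
- **Carry-over will occur.** Nothing in the documents shows that it does.
- **The battery follows immediately on eating.** Section 5.2.2 gives a next-day return for the washout session; no interval is stated for the final session.
- **Debriefing adds bias.** It comes after the battery.

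None of these replies gives the planned tests a way to establish direction for the four exposed measures.

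**Conclusion.** The point holds for interpretation of the secondary analyses. The 7-to-2 split is a matter of record in Table 2. For satiety responsiveness, plate clearing, food choice motives and compensatory health beliefs, a non-zero indirect effect or interaction cannot be assigned a direction, and the plan would nonetheless declare mediation or moderation.

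The size is conditional on two quantities that the documents do not supply: k, and any true SEP difference on the measure. Without such a difference, false mediation stays at or below about 9% for k up to 0.3 at N = 60 and an SEP difference in the PSE of 0.7 SD. The high figures need both a 0.5 SD difference and k of 0.2 or more. The moderation figures need only k.

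The primary analysis and the sample size are unaffected. The timing does not by itself show that the questionnaires must be moved.

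**What to change.** Add to 7.5.1:

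- For satiety responsiveness, plate clearing, food choice motives and compensatory health beliefs, a non-zero indirect effect or a significant interaction is reported as an association with the PSE of undetermined direction. It is not declared mediation or moderation, because these measures are first taken after both study days.
- Mediation wording is kept for portion size appropriateness and inhibition, which are taken at screening.
- For impulsivity, food insecurity and childhood resources, the late timing is noted alongside the result.

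The cost is wording, plus weaker claims for four secondary measures. No procedure, visit or sample size changes.

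Moving the four questionnaires to screening is an option for the sponsor to weigh against priming and the cover story; it is not a required change. If the battery stays where it is, the analysis cannot recover direction, so the wording above should be fixed before the data are analysed.

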7.5.2. Hunger and fullness

To investigate whether portion size reduction is associated with increased hunger/decreased fullness repeated-measures t-tests will be used to test the effect of portion size (categorical: larger, smaller; within-subject), on AUC for hunger and fullness.

7.5.3. Physical activity

To check whether the participants followed the instructions properly, we will investigate whether portion size reduction is associated with compensatory reductions in physical activity. A repeated-measures t-test will be used to test the effect of portion size (categorical: larger, smaller; within-subject) on the number of active minutes per day.

7.5.4. Study experience

We will report liking, familiarity, and normality ratings for each portion-size manipulated dish. We will also report the number of participants (total and in each group) who declared being aware of the portion-size manipulation and compare their observed awareness to chance expectation and to observed awareness of participants who declared not to be aware of the portion size manipulation (Chi-square test).

7.6. Sample size

In a previous study that used the same basic methodology but investigated the PSE over a 5-day period [39], the main effect of portion size on daily energy intake was partial $\eta^2 = 0.41$ – considered a statistically large effect size. From other studies examining shorter time frames, the effect of portion size on energy intake is medium-sized [7, 57]. To be conservative we will power the present study to be able to detect a small to medium size main effect of portion size on daily energy intake ($f=0.175$, $p < .05$, 85% power, within-subject correlation of 0.7 conservatively estimated from [39]), resulting in a minimum sample size of 46 participants. As there is limited evidence on the size of moderating effect of SEP on portion size, this sample size also provides adequate power to detect the same small to medium sized portion size and SEP interaction (within-between-subject interaction) on energy intake. Due to on-going COVID restrictions there is uncertainty over recruitment rates and it may be plausible to recruit more participants into the study. If it is feasible in the time frame of the project, we will aim to recruit up to a further 14 participants, resulting in a final $N=60$. This decision will be made prior to conducting any data analyses. Increasing sample size by approximately 30% would address uncertainty for power analysis parameters (e.g. a smaller than

anticipated sized effect being observed in the study) by increasing power. Furthermore, empirical estimates of sample sizes needed for reasonable power (e.g. 80%) in mediation analyses indicate that a sample of ≈ 60 would be sufficient to detect mediation through pathways that are medium and above in statistical size using bias-corrected bootstrap tests [40].

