7. STATISTICAL ANALYSIS

All statistical analyses will be performed using SPSS (Version 26.0). The level of significance will be set at $p < 0.05$ for primary analyses and $p < 0.01$ for secondary analyses to account for multiple testing.

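### The mediation power stated for about 60 participants ignores the plan's 0.01 rule and t-test gate, and section 7.5.1 fixes neither the gate threshold nor the interval level

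*Combined protocol and SAP*

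**What the plan says.** Four places in the combined protocol and SAP bear on this point.

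- **Section 7.6 (Sample size).** The committed size comes from the primary analysis, "resulting in a minimum sample size of 46 participants". The larger figure is conditional: "If it is feasible in the time frame of the project, we will aim to recruit up to a further 14 participants", which would give 60. As a further reason for 60, the section says that a sample of about that size "would be sufficient to detect mediation through pathways that are medium and above in statistical size using bias-corrected bootstrap tests". It gives no path values, no significance level and no interval level for this statement.
- **Section 7 (Statistical analysis).** A level of 0.05 applies to primary analyses. A level of 0.01 applies "for secondary analyses to account for multiple testing". No secondary analysis is exempted.
- **Section 7.5.1 (Mediation analyses), under 7.5 (Secondary analyses).** The SEP groups are first compared on each measure by t-test. Then: "If we find individual differences for any of these measures between participants of lower and higher SEP, mediation analyses will be performed". The test itself is a bias-corrected bootstrap with 5,000 samples: "Mediation will be tested by determining whether or not the confidence intervals of the indirect effects estimates contain zero". Neither the t-test threshold nor the confidence level is given.
- **Section 7.5.1, last paragraph.** If SEP does not moderate the PSE, or if "our individual difference measures do not explain moderation by SEP, we will repeat the primary analysis replacing SEP with the individual measures".

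**The concern.** The power statement describes a bootstrap test standing alone. The planned procedure has two steps: a measure must first differ between 30 and 30 participants on a t-test, and its indirect effect must then have an interval that excludes zero. If section 7 is applied as written, both steps run at 0.01. Each requirement can only lower the chance of detecting a true mediator.

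Explaining why the PSE may vary by SEP is the stated secondary objective. A reader who sees 80% beside a null mediation result will give that null more weight than it may deserve. Because the two levels are unstated, the operating characteristics of the test also remain open until someone chooses them at analysis.

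**Working it through.** **1. The plan's own figures.** The primary sample size reproduces. With f=0.175, correlation 0.7 and two measurements, λ = f²·N·2/(1−ρ) = 0.030625 × 46 × 2 / 0.3 = 9.39, which gives 85.0% power at N=46 (84.2% at N=45). The mediation figure cannot be rebuilt, because section 7.6 gives neither paths nor a level. It is plausible: equal standardised paths of 0.39 give 81% at N=60 with a 95% interval and no gate.

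**2. Inputs.** From the documents: N=60 and N=46; SEP groups split 1:1 (section 4.1); bias-corrected bootstrap with 5,000 draws; 0.01 for secondary analyses; the t-test gate. Assumed: two-sided tests, the path sizes, no direct effect of SEP on the PSE, and one mediator at a time. The benchmark, an ungated 95% interval giving about 80% at N=60, is also an assumption about what section 7.6 means.

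**3. Model.** SEP is X=±1. The mediator is M = aX + √(1−a²)·e and the PSE is Y = bM + √(1−b²)·e, so a and b are standardised. The SEP difference on the mediator is d = 2a/√(1−a²); for a=0.39, d = 0.78/0.921 = 0.85. Each case used 4,000 to 20,000 simulated trials, so the Monte Carlo standard error is at most √(0.5×0.5/4000) = 0.8 points.

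**4. Results.** Power in %, at N=60 except for the last column.

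| a / b | ungated, 95% | gate .05, 95% | gate .01, 95% | gate .05, 99% | gate .01, 99% | gate .01, 99%, N=46 |
|---|---|---|---|---|---|---|
| .33/.50 | 80.3 | 74.6 | 52.0 | 58.3 | 48.8 | 30.9 |
| .34/.444 | 80.1 | 73.9 | 52.3 | 54.6 | 46.1 | 28.9 |
| .36/.416 | 80.9 | 76.1 | 57.3 | 54.6 | 47.9 | 28.9 |
| .39/.39 | 80.8 | 77.4 | 62.8 | 55.2 | 49.8 | 31.3 |
| .42/.376 | 80.2 | 78.4 | 67.3 | 55.6 | 51.4 | 32.8 |
| .45/.376 | 80.8 | 79.6 | 72.4 | 57.3 | 54.7 | 36.8 |
| .50/.38 | 80.2 | 79.8 | 77.2 | 58.5 | 57.5 | 41.5 |
| .55/.396 | 80.8 | 80.8 | 80.1 | 59.9 | 59.7 | 45.7 |
| .60/.415 | 81.1 | 81.1 | 81.0 | 60.7 | 60.7 | 47.7 |

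A second, separately coded simulation gave 82, 78, 64, 55 and 50 for .39/.39 at N=60, in the same column order. Adding a direct effect of 0.14 to paths of 0.38 gave 80.5% ungated with a 95% interval and 47.2% under 0.01 for both steps.

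**5. Where the loss arises.** When the SEP–mediator path is small, the gate dominates: for .33/.50 a 0.01 gate alone takes 80.3 − 52.0 = 28.3 points, and the 99% interval a further 3.2. When that path is large, the gate costs almost nothing and the interval does the damage: for .60/.415, 81.1 − 60.7 = 20.4 points.

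**6. What keeps 80% under the full 0.01 rule.** At N=60, equal paths of 0.48 give 79.8% and of 0.49 give 82.4%. A path of 0.48 means d = 0.96/0.877 = 1.1. Equal paths of 0.39 need about N=90 (79.4% and 80.8% in two runs).

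**7. Error rate.** With a=0.39 and b=0 at N=60, a 0.01 gate gives a false-positive rate per mediator of 1.7% with a 99% interval and 6.1% with a 95% interval (10,000 trials). The 99% interval is closer to section 7's level, though still above it.

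**The case against.** The strongest reply is that section 7.5.1 never asks for a 99% interval. A reader who takes a 0.05 gate and a 95% interval gets 74–81%, and the statement in section 7.6 roughly holds. This stands: the loss depends on levels that the plan does not give, and a flat claim that mediation power is about 50% would go beyond the documents. But section 7 exempts no secondary analysis, so the lenient reading also needs a sentence that is not there.

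Second, the path pairs were chosen to sit near 80% under the most lenient test, so any stricter test must lower them, and section 7.6 covers larger paths too. That is fair. Equal paths of 0.50 keep 85% under the full rule at N=60. The shortfall is at the lower edge of what section 7.6 covers, but that edge is part of its claim.

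Third, a reader might infer that the plan promises mediation power at 46 participants. It does not: the sentence only supports the optional extension to 60. The N=46 figures show what the committed size would give; they do not contradict a stated figure.

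Fourth, a reader might infer that the move to moderation analyses treats a null as proof of no mediation. The moderation analyses are prespecified in section 2, they discard nothing, and section 7.5.1 begins that paragraph in terms of not finding evidence. The risk lies in how a null is read.

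**Conclusion.** The point holds in conditional form. Section 7.6 states mediation power without accounting for the 0.01 rule or the gate, and section 7.5.1 leaves both levels open. For paths of 0.39 the choice of levels alone moves power at N=60 from 77% to 50%. Over the nine pairs, applying section 7 to both steps leaves about 46–61%; under the other two readings in which the interval is 95%, the range is 52–81% (0.01 gate) or 74–81% (0.05 gate).

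These figures rest on assumed paths, on an ungated 95% interval as the benchmark, and on single-mediator models. Section 7.5.1 also plans a model with all mediators together, which was not simulated. The documents do not support a conclusion that the trial as a whole is underpowered: the primary calculation reproduces and is untouched. This is a correction worth making for a secondary objective.

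**What to change.** Two edits to the text, with no new data.

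1. **Section 7.5.1.** State, before analysis, the threshold for the SEP group comparisons and the level of the bootstrap intervals. Applying section 7 as written means p<0.01 and 99% intervals. If 95% intervals are intended, say that mediation is exempt from the 0.01 rule.

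2. **Section 7.6.** Replace the mediation sentence with the power for the chosen levels and the assumed paths. Under 0.01 for both steps, for example:

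> With both standardised paths 0.39 (an assumption), single-mediator power is about 50% at N=60 and about 31% at N=46; about 80% at N=60 needs both paths of about 0.48. The model with all mediators together was not simulated. A failed group comparison, or an interval that includes zero, is inconclusive and not evidence of no mediation.

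For the same paths, the figures to insert would be about 63% (N=60) and 44% (N=46) with a 0.01 gate and a 95% interval, or 77% and 61% with a 0.05 gate and a 95% interval.

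The cost is a less favourable stated power for a secondary objective. The edits recover no power; they make the stated figure describe the test that will be run.
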